4.6 Additional Endpoints

The following secondary objectives are intended to support product labeling. The endpoints will be tested in sequential fashion using the Holms step-down procedure for type-I error rate correction if and only if the primary objective passes according to the non-inferiority criteria outlined above. At the conclusion of the trial, the secondary endpoints intended for product labeling will be ordered sequentially from most significant to least significant. The endpoints will then be tested in order at adjusted levels of significance (i.e. E1: 0.05/k, E2: 0.05/k-1; E3: 0.05/k-2; E4: 0.05/k-3; E5: 0.05/k-4;, where k=number of specified endpoints). Once an endpoint fails, all following endpoints will not be tested. Following is a list of secondary endpoints intended to support product labeling:

- Evaluation of the proportion of subjects requiring re-operation and re-intervention through 6 months. The following hypothesis will be tested:

$$H: P_C - P_T > -\delta$$

where P_T and P_C represent proportions of subjects requiring re-operation or re-intervention through 6 months post treatment. The Aquablation group will be declared to be non-inferior to TURP if it can be established that the difference is within the non-inferiority margin of $\delta = 0.10$. The statistical test will be a z-test using pooled variance estimate and no continuity correction. In the case of small counts, an exact procedure will be used. Descriptive statistics and 95% confidence intervals will be calculated.

- Evaluation of the proportion of sexually active subjects reporting a worsening of sexual function through 6 months defined as a decrease of 6 points or more on the IIEF-5 (part of the IIEF-15) or a decrease of 2 points or more on the MSHQ-EjD questionnaires. The following hypothesis will be tested:

$$H_0: P_T = P_C$$

$$H_a: P_T < P_C$$

where P_T and P_C represent proportions of subjects with worsening score on the IIEF-5 and/or the MSHQ-EjD from baseline through 6 months post treatment. The statistical test for superiority will be a z-test using pooled variance estimate and no continuity correction. In the case of small counts, an exact procedure will be used. Descriptive statistics and 95% confidence intervals will be calculated.

- Evaluation of the mean length of hospital stay in the treatment groups. The following hypothesis will be tested:

$$H: \mu_T - \mu_C > 0$$

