## **6 Secondary Endpoint Assessments**

Six secondary endpoints, described below, are intended for marketing claims: 3 are based on 6-month results and 3 are based on perioperative results. Statistical testing for the 6-month secondary endpoints will only occur after data collection is complete.

Tests based on 6-month data:

1. Reoperation or re-intervention within 6 months. Reoperation means any surgical procedure on the lower urinary tract to treat problems potentially related to BPH. Re-intervention means any invasive procedure (e.g., cystoscopy) to evaluate problems potentially related to BPH. Re-intervention excludes TRUS and urodynamics, which are required study evaluations during follow-up. Re-intervention also excludes catheterization (which is not a surgical procedure) for acute urinary retention. The proportion of subjects with this endpoint will be compared using Fisher's exact test. Differences in proportions will be calculated with `testbinomial` from the `gsDesign` package. A 10% non-inferiority hypothesis (like the primary safety endpoint, of which this is a component) will be used and superiority will be explored after non-inferiority is shown.
2. The proportion of sexually active subjects reporting a worsening of sexual function through 6 months on either the IIEF or the MSHQ-EjD questionnaires. A subject is counted as having worse sexual function if IIEF-5 (part of IIEF-15) is decreased by at least 6 points or MSHQ is decreased by at least 2 points. The two-point threshold for MSHQ is close to

the value that distinguishes affected from unaffected men.\* Both IIEF and MSHQ assume that a man is sexually active. If the subject reports that he is not sexually active for the time period assessed, these threshold decreases cannot be met by definition. Differences in proportions will be calculated as described above. Superiority will be tested.

3. The proportion of subjects with major adverse urologic events (MAUE). MAUE is defined as any subject with a serious device- or serious procedure-related AE judged to be urologic through 6 months. Whether an event meets this endpoint is judged using the study's SAE definition and relatedness, both of which are adjudicated by the CEC. Differences in proportions will be calculated as described above. A 10% non-inferiority hypothesis (like the primary safety endpoint) will be used.

Tests based on perioperative data:

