4. Length of hospital stay (days) in the treatment groups. Proportional odds logistic regression will be used. A NIM of ½ a day will be used. Additional analyses will be done stratifying for geography (e.g., Europe vs. US vs. Australia/New Zealand), as it is known that LOS is generally shorter in the US.
5. Length of operative time (minutes) in the treatment groups, defined as time from pre-treatment visualization to insertion of indwelling catheter (IDC), will be compared using a t test. Simple superiority will be tested.
6. Length of resection time (minutes) in the treatment groups, defined as start of first pedal activation to end of last pedal use for either A or T, will be compared using a t test. Simple statistical superiority will be evaluated.

The 6 endpoints listed above will be tested in sequential fashion using the Holm step-down procedure for type-I error rate correction. The testing will be done only if the primary safety and effectiveness endpoints meet the study's non-inferiority goals. Secondary endpoints listed above will be ordered sequentially from most significant to least significant. The endpoints will then be tested in order at adjusted levels of significance (i.e. E1: 0.05/k, E2: 0.05/k-1; E3: 0.05/k-2, etc., where k=number of specified endpoints). Once an endpoint fails, all subsequent secondary endpoints will not be statistically tested.

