## 7 Additional Endpoint Assessments

The following additional endpoints, evaluated using the PP cohort, are pre-specified but are not intended to support product labeling. Comparisons of proportions described below will be done using methods similar to those described for the reoperation/reintervention secondary endpoint. Comparisons of continuous variables will use a t test unless otherwise described. Testing of continuous variables will examine superiority, and in some cases, non-inferiority. Superiority tests will be 2-sided ( $\alpha=0.05$ ). Non-inferiority tests will be one-sided ( $\alpha=0.025$ ).

1. Proportion of subjects with Clavien-Dindo classification of Grade 2 or higher or any Grade 1 with persistent disability (e.g. ejaculatory disorder or erectile dysfunction) at 30 days, 6 months, and 1 year. 6-month and 1-year calculations will be performed only when full datasets are available. A 10% NIM will be used.

---

\* According to personal communication [name], creator of MSHQ, no published MCID for MSHQ exists.

2. Evaluation of the proportion of subjects with dysuria through the day 30 visit. Dysuria is defined as burning sensation while urinating of at least “about ½ the time” on the dysuria questionnaire. An additional comparison using proportion odds logistic regression will be performed. A 15% NIM will be used.
3. Duration of bladder catheterization (i.e., intraoperative catheter placement to removal prior to discharge) after the assigned study procedure. Duration will be compared with a t test. An NIM of ½ a day will be used.
4. Change in hemoglobin (gm/dl) (i.e., laboratory test) at discharge from baseline.
5. Reoperation or Re-intervention within 30 days, 12 months, 24 months and 36 months. For the 30-day time point, proportions will be compared with a 10% NIM. For longer time points, due to the expectation of study withdrawal, Kaplan-Meier survival analysis will be performed and a log rank test calculated.
6. Changes in the proportion of subjects using medications for BPH symptoms at month 6. Two analyses will be done. 1) an analysis of the proportion of subjects who increased doses of BPH medications or started a new BPH medication, and 2) the proportion who were able to decrease or stop doses of BPH medications. Relevant medications include alpha blockers, prostaglandin inhibitors, and phosphodiesterase inhibitors. A 10% NIM will be used.

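### The Holm ladder for the six labelling endpoints starts at 0.05/k without saying whether the p-values are one- or two-sided, and Fisher's exact test is named for a 10% margin hypothesis

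*SAP*

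**What the plan says.** SAP section 6 defines the family: "The 6 endpoints listed above will be tested in sequential fashion using the Holm step-down procedure". The levels follow: "The endpoints will then be tested in order at adjusted levels of significance (i.e. E1: 0.05/k", then 0.05/k-1, 0.05/k-2 and so on, stopping at the first failure. Protocol 4.6 uses the same scheme ("The endpoints will be tested in sequential fashion using the Holms step-down procedure for type-I error rate correction") and the same 0.05. Neither section states sidedness. Both open the family only after the primary non-inferiority criteria are met.

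In the SAP the family mixes two kinds of test:

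- Margin tests: reoperation or re-intervention ("A 10% non-inferiority hypothesis (like the primary safety endpoint, of which this is a component) will be used"), MAUE ("A 10% non-inferiority hypothesis (like the primary safety endpoint) will be used") and hospital stay (half a day).
- Superiority tests: sexual function, operative time and resection time.

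For reoperation the SAP says "The proportion of subjects with this endpoint will be compared using" Fisher's exact test. It then assigns differences in proportions to testBinomial and states the 10% hypothesis. Endpoints 2 and 3 refer back to that description. Protocol 4.6 names a pooled z-test for reoperation instead.

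Elsewhere the non-inferiority level is explicit. Protocol 4.2 and 4.3 use one-sided 0.025 for the two primaries. SAP 5.1 and 5.2 use a two-sided 95% interval, which is the same thing. SAP 7 covers the non-labelling endpoints: "Non-inferiority tests will be one-sided" at 0.025, with superiority two-sided at 0.05.

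**The concern.** A test against a margin looks in one direction, so its ordinary p-value is one-sided. Compared with a ladder whose total is 0.05, it is held to a family level twice the 0.025 that governs the primaries and the non-labelling endpoints. The endpoints meant for marketing claims would then carry the weakest error control in the plan.

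Borrowing the SAP 7 convention does not help. Non-inferiority p-values would be one-sided and superiority p-values two-sided, yet all six would be ranked together against one set of thresholds. The order of testing, and therefore which claims are reached, would depend on a choice that the SAP does not make.

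The Fisher wording raises a different risk. Its null is equal proportions. If its p-value entered the ladder, a device that is truly no worse than TURP could fail its non-inferiority claim and, because testing stops at a failure, take later endpoints down with it.

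**Working it through.** **1. The plan's ladder.** With k = 6 and family level 0.05, the thresholds 0.05/(6−i), for i = 0 to 5, are 0.0083, 0.0100, 0.0125, 0.0167, 0.0250 and 0.0500. This matches SAP 6 if 0.05/k-1 is read as 0.05/(k−1). At family level 0.025 they are 0.0042, 0.0050, 0.0063, 0.0083, 0.0125 and 0.0250.

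**2. The plan's working convention.** Protocol 4.4 gives 156 evaluable and 177 enrolled from rates of 65% and 40%, 80% power, 2:1 allocation and 12% loss. The pooled proportion is (0.65 + 2×0.40)/3 = 0.4833. The uncorrected control size is

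[1.96√(3×0.4833×0.5167) + 0.8416√(2×0.65×0.35 + 0.40×0.60)]² / (2×0.25²) = 2.398²/0.125 = 46.0.

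The continuity correction gives (46.0/4)[1 + √(1 + 6/(46.0×2×0.25))]² = 51.8, so 52 + 104 = 156, and 156/0.88 = 177.3. One-sided 0.05 gives 42 + 84 = 126. The plan was therefore sized at one-sided 0.025, which is two-sided 0.05.

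**3. Family-wise error if one-sided p-values are entered.**

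| Situation | Holm at 0.05 | Holm at 0.025 |
|---|---|---|
| Six independent true nulls, 1−(1−α/6)^6 | 0.0490 | 0.0247 |
| Six true nulls, correlation 0.5 (simulated, 400,000 runs) | 0.039 | 0.020 |
| Three margin nulls true, superiority endpoints already rejected, independent, 1−(1−α/3)^3 | 0.049 | 0.025 |
| One margin null left at the last step | 0.050 | 0.025 |

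**4. If two-sided p-values are entered at 0.05/k.** The simulated rate of false claims in the favourable direction is 0.020 to 0.021 at correlation 0.5. There is no doubling.

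**5. A single claim.** On the one-sided reading, steps 1 to 4 are stricter than an unadjusted 0.025, step 5 equals it, and only step 6 (0.05) exceeds it. For example, a margin endpoint reached last with one-sided p = 0.03 has z = 1.88. That passes 0.05, yet 1.88 < 1.96, so its two-sided 95% interval includes the margin. The same result would fail the primary safety rule in SAP 5.1.

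**6. Mixed scales.** Take z = 2.5. For a margin endpoint the one-sided p is 0.0062, below 0.0083, so it passes the first step. For a superiority endpoint the two-sided p is 0.0124, above 0.0083, so it fails. The strength of evidence is the same and the outcome differs.

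**7. Fisher against a margin.** For illustration only, assume equal reoperation rates of 4/104 and 2/52 (3.8% each). Fisher's two-sided p is 1. Against the 10% margin the unpooled standard error is √[0.0385×0.9615×(1/104 + 1/52)] = 0.0327, so z = 0.10/0.0327 = 3.06 and one-sided p = 0.001. A score test that estimates the rates under the margin gives z = 2.80 and p = 0.0026. Both clear even 0.025/6 = 0.0042. Fisher would block a claim that the data support.

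**The case against.** The strongest reply is that SAP 6 never says one-sided, and 0.05 is simply the two-sided form of the plan's 0.025. Several places favour that reading. Protocol 4.6 asks for 95% intervals on each secondary endpoint that it describes. The SAP judges both primaries by two-sided 95% intervals and likens the two 10% secondary hypotheses to the primary safety endpoint. The sample size also reproduces only at that level. This stands as a plausible intention, and on that reading the level needs no change. It does not settle the text: the explicit convention in SAP 7 covers only the non-labelling endpoints, and Protocol 4.6 writes the sexual-function alternative in one direction.

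Three stronger readings are tempting, and the documents do not support them.

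- A reader might infer that every non-inferiority claim gets twice the intended error. The factor of two is family-wise, or applies to a claim tested last.
- A reader might say that Fisher can never rule out a 10-point excess. A significant result in favour of Aquablation would do so. The fault is that the test does not address the margin, which here makes it too strict. The SAP also names testBinomial in the next sentence, and SAP 5.1 uses that function for non-inferiority p-values, so the right tool is already in the plan.
- A reader might infer from "Statistical testing for the 6-month secondary endpoints will only occur after data collection is complete" that the perioperative endpoints are to be tested earlier. No text schedules that. SAP 5.6.1 allows an interim report that summarises secondary endpoints, but the Holm paragraph orders all six together after both primaries pass.

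**Conclusion.** The point holds as an unspecified scale that permits inflation. It does not hold as a demonstrated doubling. If one-sided p-values enter the printed ladder, one-sided family-wise error is up to 0.05, against 0.025 for non-inferiority elsewhere. It is 0.049 under independence and 0.039 at correlation 0.5, and a last-tested endpoint is judged at one-sided 0.05. If the SAP 7 convention is carried over, the ranking favours the margin endpoints. If all p-values are two-sided, the level is already right.

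The Fisher wording is a separate defect that does not depend on sidedness: an equality test is attached to a margin hypothesis. The size of its effect depends on event rates that the documents do not give; the 3.8% above is an assumption.

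Both matters affect labelling claims only, not the primary conclusion. They are worth correcting because the correction is cheap.

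**What to change.** In SAP 6 and Protocol 4.6:

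- State one scale for all six p-values: one-sided with Holm at 0.025/6, 0.025/5, …, 0.025, or the equivalent two-sided p-values at 0.05/6, 0.05/5, …, 0.05. Write the denominators as (k−1), (k−2).
- For reoperation and MAUE, enter the testBinomial p-value computed against the 10% margin. Keep Fisher only for the follow-on superiority look at reoperation.
- Run Holm once, when the primary results and all six p-values are available.
- Reconcile the family between the documents. Protocol 4.6 gives no test for MAUE and tests hospital stay for superiority; the SAP gives stay a half-day margin.

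The cost is wording, plus thresholds for the margin endpoints half as large as a one-sided reading of the present ladder would allow. Protocol 3.3 marks these endpoints as already reported. If that analysis is final, record which sidedness was used and show whether each claim survives on the consistent scale.

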## 7 Additional Endpoint Assessments

The following additional endpoints, evaluated using the PP cohort, are pre-specified but are not intended to support product labeling. Comparisons of proportions described below will be done using methods similar to those described for the reoperation/reintervention secondary endpoint. Comparisons of continuous variables will use a t test unless otherwise described. Testing of continuous variables will examine superiority, and in some cases, non-inferiority. Superiority tests will be 2-sided ( $\alpha=0.05$ ). Non-inferiority tests will be one-sided ( $\alpha=0.025$ ).

1. Proportion of subjects with Clavien-Dindo classification of Grade 2 or higher or any Grade 1 with persistent disability (e.g. ejaculatory disorder or erectile dysfunction) at 30 days, 6 months, and 1 year. 6-month and 1-year calculations will be performed only when full datasets are available. A 10% NIM will be used.

---

\* According to personal communication [name], creator of MSHQ, no published MCID for MSHQ exists.

2. Evaluation of the proportion of subjects with dysuria through the day 30 visit. Dysuria is defined as burning sensation while urinating of at least “about ½ the time” on the dysuria questionnaire. An additional comparison using proportion odds logistic regression will be performed. A 15% NIM will be used.
3. Duration of bladder catheterization (i.e., intraoperative catheter placement to removal prior to discharge) after the assigned study procedure. Duration will be compared with a t test. An NIM of ½ a day will be used.
4. Change in hemoglobin (gm/dl) (i.e., laboratory test) at discharge from baseline.
5. Reoperation or Re-intervention within 30 days, 12 months, 24 months and 36 months. For the 30-day time point, proportions will be compared with a 10% NIM. For longer time points, due to the expectation of study withdrawal, Kaplan-Meier survival analysis will be performed and a log rank test calculated.
6. Changes in the proportion of subjects using medications for BPH symptoms at month 6. Two analyses will be done. 1) an analysis of the proportion of subjects who increased doses of BPH medications or started a new BPH medication, and 2) the proportion who were able to decrease or stop doses of BPH medications. Relevant medications include alpha blockers, prostaglandin inhibitors, and phosphodiesterase inhibitors. A 10% NIM will be used.
7. IPSS change score during follow-up (1 week, 1, 3, 6, 12, 24 and 36 months). Repeated measures analysis of variance (RMANOVA) will be used, with additional models that include baseline IPSS as a covariate. This analysis accounts for all available measurements and correlation of measurements within subjects. The mean differences across groups will be determined and the confidence limits from the regression model compared with the study-specific NIM. A treatment × time interaction will be explored as well. The purpose of this analysis is to evaluate whether the IPSS change score across all time points is non-inferior in A compared to T. The same NIM will be used as described for the primary effectiveness endpoint. If non-inferiority is shown, superiority will be tested. All available time points will be used up to month 36.
8. IPSS-QoL change scores (1 week, 1, 3, 6, 12, 24 and 36 months). A similar method as that with IPSS change score will be used and a 1-point NIM will be assumed.
9. Qmax change scores at 1, 3, 6, 12, 24 and 36 months. RMANOVA will be used.
10. PVR change scores at 1, 3, 6, 12, 24 and 36 months. RMANOVA will be used.
11. Proportion of subjects with device- or procedure-related adverse event. Proportions compared as described for primary safety endpoint.
12. Pelvic pain intensity level, population mean and change score mean, measured on a 0-10 numeric rating scale. Population score distributions will be compared with a Wilcoxon signed rank test. Change scores will be compared with a Wilcoxon test or t test. A non-inferiority margin of 2 points will be used.

13. EQ-5D time trade-off index (TTO) change scores during follow-up (7 days, and 1, 3, 6, 12, 24 and 36 months). TTO will be calculated using study data combined with available country-specific norms. RMANOVA will be used.
14. ISI at baseline, at post-op, 7 days, 1, 3, and 6 months. RMANOVA will be used.
15. IIEF-15 at baseline, and 7 days, 1, 3, 6, 12, 24 and 36 months. RMANOVA will be used.
16. MSHQ-EjD at baseline, 7 days, 1, 3, 6, 12, 24 and 36 months. RMANOVA will be used.
17. WPAI:US at baseline, 7 days, 1, 3, 6, 12, 24 and 36 months. Specifically, among those subjects who are currently working, the number of hours missed due to urinary symptoms will be compared. Given a large expected number of zeroes, a non-distributional method such as Wilcoxon's test will be used.
18. Pdet@Qmax at baseline and 6 months. This continuous outcome will be evaluated with a t test.
19. Change in categorization of subjects from obstructed to unobstructed or unobstructed to obstructed at month 6 in those subjects in whom urodynamics was performed. (Urodynamics is an optional test.) The determination of "obstructed" and "unobstructed" is based on urodynamics values and Chapple. Specifically, AG (Abrams-Griffith) number is calculated as  $AG = Pdet@Qmax - 2 * Qmax$ . AG is interpreted as:
  - If  $AG \geq 40$ : obstructed
  - If  $AG < 20$ : not obstructed
  - If  $20 \leq AG < 40$ : calculate slope =  $(Pdet@Qmax - Pvoid0) / Qmax$ . If slope  $> 2$ , obstructed, else unobstructed.

Changes from baseline to follow-up within a treatment group will be calculated with a McNemar's test. Conditional odds ratio will be calculated according to Suzuki.
20. Use of cautery immediately post Aquablation. The proportion in which cautery was used and the distribution of cautery time will be calculated. Cautery use will be assessed as minutes from cautery start to stop and total amount of "on time".
21. Proportion of subjects in whom re-catheterization was needed between discharge after the index procedure and month 3. Re-catheterization is defined as the need to place a urinary catheter in the bladder for symptoms related to BPH. This excludes re-catheterization for study purposes or for purposes unrelated to LUTS.
22. Amount of irrigation fluid used intraoperatively (liters). A t test or Wilcoxon's test will be used to evaluate mean differences.
23. Proportion of subjects in whom postoperative bladder irrigation was started.
24. Prostate size reduction from baseline to 3 months as measured TRUS. A t test will be used for the comparison.
25. Relationship between prostate size reduction and change in various measurements (IPSS, etc.).

26. Relationship between prostate size and procedure or resection times. It is expected that procedure times will be related to prostate size in T but not A. Linear models will be run for each treatment group. In addition, a linear model will be run for all subjects that includes an interaction term.

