2 CLINICAL INVESTIGATIONAL PLAN

2.1 Background

Benign prostatic hyperplasia (BPH), or enlargement of the prostate due to benign growth of glandular tissue, is a very common disease of older men. Prostatic tissue may compress the urethral canal, causing partial or sometimes complete obstruction of the prostatic urethra, which interferes with the normal flow of urine. Symptoms of BPH include urinary hesitancy, frequent urination, dysuria, increased risk of urinary tract infections and urinary retention.

Therapy for BPH includes medication and various surgical approaches. While medication is first-line therapy, many men do not have adequate responses to treatment. Surgical approaches include transurethral resection of the prostate (TURP) and other less invasive approaches such as transurethral microwave thermotherapy (TUMT) or transurethral needle ablation (TUNA). TURP involves invasive removal of prostate tissue using electrocautery and/or sharp dissection. While TURP remains the gold standard for treatment, it carries risks, including bleeding, clot retention/colic, bladder wall injury, hyponatremia (water intoxication), bladder neck contracture, urinary incontinence, retrograde ejaculation, and erectile dysfunction. Additional techniques using lasers or electrocautery that either ablate or enucleate the adenomatous tissues have been developed to improve the efficiency and reduce the morbidity of TURP.

PROCEPT BioRobotics has developed the AQUABEAM System, utilizing a high-velocity saline jet designed to selectively cut prostatic glandular tissue, a minimally invasive surgical procedure dubbed Aquablation. The AQUABEAM System is currently under clinical investigation for the treatment of lower urinary tract symptoms associated with benign prostatic hyperplasia (BPH).

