2.29 Study Assessments

The schedule of assessments is shown in **Table 2**. Details of selected assessments are provided below:

Table 2. Schedule of Assessments

Evaluation	Baseline w/in 90 days of Tx	Tx	Post-Op	Follow-Up Clinic Visits						
				1 wk (+/-3 days) (phone)	1 mon (+/-5 days)	3 mon (+/-10 days)	6 mon (+/-30 days)	12,24,36 mon (+/- 60 days)	48 mon (+/- 60 days)(pho ne)	60 mon (+/- 60 days)
Medical history	X									
Vital Signs /Urological Examination	X				X ⁷ (vital signs only)					
PSA	X						X	X		X
Serum Blood Test for CBC and electrolytes	X		X ⁴							
Urine for M/C/S	X	X ¹								
Qmax and PVR	X				X	X	X	X		X
Cystourethroscopy	X (within 3 months)	X ²								
Urodynamics (at selected sites)	X (within 6 months)						X			
Pain NRS and Dysuria Score		X ³	X ⁵	X	X	X				
Incontinence Severity Index	X		X ⁵	X	X	X	X			
Blinding Questionnaire			X	X	X	X	X	X		
IPSS, EQ-5D, IIEF-15, MSHQ-EjD, WPAI:US	X			X	X	X	X	X	X ⁶	X ⁶
TRUS	X (within 6 months)	X				X				
DRE	X					X				
Concomitant Medication	X	X	X	X	X	X	X	X	X ⁸	X ⁸
Concomitant Procedure			X	X	X	X	X	X		
Procedure information		X								
Adverse events		X	X	X	X	X	X	X	X ⁹	X ⁹

¹ Urine dipstick analysis to be done within 72 hours prior to procedure

² Rigid cystoscopy is required

³ To be assessed immediately prior to the procedure

⁴ Done in the recovery room

⁵ To be completed post-catheter removal

⁶ IPSS, IIEF15, and MSHQ-EjD only

⁷ If subject has intraoperative or postoperative cardiovascular event

⁸ Only urological adverse events related medication and all BPH medication

⁹ Only urological adverse events

Medical history. During the baseline assessment, the investigator or coordinator will record details of medical history as they relate to BPH.

Vital Signs / Urological examination. At baseline the investigator will measure vital signs and perform a focused urological examination and document any preoperative abnormalities. Vital signs will be collected at the 1-month visit if the subject had an intraoperative or post-operative cardiovascular adverse event.

Serum Blood Test. A blood sample will be collected to measure PSA, complete blood count (CBC) and electrolytes (to include at least levels of sodium, blood urea nitrogen and creatinine). Test timing is shown in the schedule of assessments.

Urine for M/C/S. A mid-stream urine sample will be collected at baseline, and repeated within 72 hours prior to the procedure to exclude current urinary tract infection.

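### The day-30 dysuria comparison (SAP Section 7, item 2) leaves the pre-procedure dysuria score unused, so it cannot separate prior dysuria from dysuria that the procedure causes

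*SAP*

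**What the plan says.** SAP Section 7, item 2 is titled "Evaluation of the proportion of subjects with dysuria through the day 30 visit". "Dysuria is defined as burning sensation while urinating of at least" about half of the time on the dysuria questionnaire. This is a threshold on the score itself, not a change, a worsening or a new onset. For the comparison, "A 15% NIM will be used"; the section's introduction adds that "Non-inferiority tests will be one-sided", at 0.025. Proportions are compared as for the reoperation endpoint in SAP Section 6, which uses testBinomial from gsDesign. Item 2 then says: "An additional comparison using proportion odds logistic regression will be performed". No covariate is named. All Section 7 endpoints are "evaluated using the PP cohort, are pre-specified but are not intended to support product labeling".

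Protocol Section 3.3 carries the same endpoint, also without a baseline condition. In Protocol Section 2.29, Table 2, the pain and dysuria scores share one row, with assessments on the treatment day, post-operatively, at 1 week, 1 month and 3 months. Footnote 3 fixes the treatment-day assessment: "To be assessed immediately prior to the procedure". Protocol Section 2.1 notes: "Symptoms of BPH include urinary hesitancy, frequent urination, dysuria".

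**The concern.** Dysuria during the first month is a tolerability outcome, and the natural question is how much of it the procedure causes. A man who already had burning above the threshold before surgery can count as an event whatever was done to him. In a superiority test, events common to both arms cost power. In a non-inferiority test, they can pull the arm difference toward zero and make it easier to pass.

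The plan deals with prior status for comparable outcomes:

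- Pain, which shares the dysuria row in Table 2, gets a change score (SAP Section 7, item 12).
- Hemoglobin is analyzed as change from baseline (item 4).
- IPSS models include the baseline score as a covariate (item 7).
- Sexual function is tested as worsening (SAP Section 6, endpoint 2).
- For incontinence, Protocol Section 2.29 sets out to isolate new cases from pre-existing ones.

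Dysuria has a pre-procedure score too, but item 2 makes no use of it.

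**Working it through.** **Figures in the plan.** The documents give no expected dysuria rate, power or derivation of the 15% margin, so there is no dysuria figure to reproduce. The sample size used below can be checked. Protocol Section 4.4 assumes 65% against 40% at 80% power with 2:1 allocation. With a continuity correction this needs 52 TURP subjects, hence 104 + 52 = 156 evaluable. Then 156 / 0.88 = 177.3, which matches the stated 177 (118 and 59).

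**Inputs.** Margin 15 points and one-sided 0.025 (SAP Section 7); 118 v 59 randomized or 104 v 52 evaluable (Protocol Section 4.4). The per-protocol cohort size is not known in advance. Three quantities are assumed because the documents do not give them: prevalence b of dysuria before the procedure (10%, 20%, 30%), the TURP rate of new dysuria (20% to 50%), and the arm difference e among men with prior dysuria.

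**Formula.** With d the arm difference among men without prior dysuria, the all-men difference is

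D = (1 - b) × d + b × e.

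**Case 1: men with prior dysuria count equally in both arms (e = 0).** Put d = 15 points:

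| b | D = (1 - b) × 15 | New-onset difference equivalent to D = 15: 15 / (1 - b) |
|---|---|---|
| 0% | 15.0 | 15.0 |
| 10% | 13.5 | 16.7 |
| 20% | 12.0 | 18.8 |
| 30% | 10.5 | 21.4 |

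The chance of declaring non-inferiority at d = 15 points was obtained by exact binomial enumeration. All men with prior dysuria are counted as events, so the arm rates are b + (1 - b) × p for TURP and b + (1 - b) × (p + 0.15) for Aquablation. Here p runs from 20% to 50% for the score test and from 30% to 50% for the Wald limit.

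| b | Score test, 118 v 59 | Score test, 104 v 52 | 95% Wald limit, 118 v 59 |
|---|---|---|---|
| 0% | 2.5-2.8% | 2.5-2.8% | 2.3-2.6% |
| 10% | 3.8-4.2% | 3.7-4.2% | 3.8-4.2% |
| 20% | 5.8-6.1% | 5.5-5.8% | 5.9-6.6% |
| 30% | 8.4-8.7% | 7.8-8.2% | 8.5-10.1% |

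The score test is taken as the closer match to the function named in the SAP. The Wald column shows the sensitivity to that choice.

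**Case 2: the arms also differ among men with prior dysuria.** Take b = 20% and d = 15:

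- e = 5: D = 0.8 × 15 + 0.2 × 5 = 13.0 points (partial dilution).
- e = 15: D = 0.8 × 15 + 0.2 × 15 = 15.0 points (no dilution; with TURP and Aquablation rates of 80% and 95% in these men, the pass rate is about 2.5-2.7%).
- e = 25: D = 0.8 × 15 + 0.2 × 25 = 17.0 points (the opposite direction).

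Dilution therefore needs both b > 0 and e smaller than d.

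**The case against.** A reader might infer that the 15% margin is wider than the SAP states, or that the test's type I error is inflated. The documents do not support either. The margin is set on the proportion of all men with dysuria, and that is the quantity tested. Randomization balances prior dysuria in expectation, so the error against the SAP's own null stays near 2.5%. The 16.7, 18.8 and 21.4 points belong to new-onset dysuria, for which no margin is set. The higher pass rates arise when the tested difference is truly 13.5, 12.0 or 10.5 points, all inside the margin.

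Nor do the documents show that dilution occurs. Listing dysuria as a BPH symptom does not say how many trial subjects burn about half the time or more. Eligibility removes several causes (active infection, bladder calculus, recently treated or chronic prostatitis), so 20% to 30% may be high. Nothing shows that men with prior dysuria count equally in both arms.

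Any dysuria during recovery is also a legitimate endpoint and matches the protocol. Replacing it with new-onset dysuria would ignore worsening in men with prior dysuria and would cost power. With no true difference, b = 30% and a new-onset rate of 40%, the score test passes about 48% of the time with all men (118 v 59). It passes about 39% of the time with only the 70% free of prior dysuria (0.7 × 118 ≈ 83 v 0.7 × 59 ≈ 41).

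These points stand. What remains is that item 2 cannot separate prior from new symptoms although the score that would do so is collected. The SAP does not forbid adjusting the proportional odds model, but neither does it plan it, whereas item 7 names its baseline covariate.

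**Conclusion.** The point holds as an improvement to an otherwise valid analysis. The all-men comparison and its 15-point margin are sound as stated. A pass should not be read as showing that new dysuria is within 15 points. On the assumptions that 10% to 30% of men have prior dysuria and count about equally in both arms, a 15-point excess in new dysuria shows as 13.5 to 10.5 points and passes about 4% of the time at the low end and 8-10% at the high end. With equal arm differences in both groups of men, the effect is nil. The consequence is limited: item 2 is one of 26 additional endpoints, is not intended to support labeling, and has no bearing on study success or on the Holm-tested secondary endpoints.

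**What to change.** In SAP Section 7, item 2:

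1. Keep the all-men proportion with its 15% margin, and say expressly that it means any dysuria, whether or not it was present before the procedure.
2. Add the pre-procedure dysuria score as a covariate in the planned proportional odds model.
3. Report as supportive the proportion with new-onset dysuria: below the threshold before the procedure and at or above it at a post-procedure visit through day 30. Show the number of men excluded, by arm.

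The cost is a few lines of SAP text and no new data. The adjusted model loses no man for having prior dysuria, only any without a pre-procedure score. The supportive proportion loses the men above the threshold beforehand, which is why it should not replace the main one. Protocol Section 3.3 marks these endpoints as already reported, so if the analyses are run now they should be labeled as added after the fact.
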